11.0 Potential Benefits to Subjects and Others

11.1 Potential Benefits to Subjects

There may be no benefit to participants in the research. Prior evidence suggests reSET-O may improve adherence with appointments, adherence to medication, and skills to avoid drug use and relapse. However, the purpose of the research is to determine whether this benefit will be observed when reSET-O is implemented within a Hub and Spoke system.

There is no benefit to the provider subjects.

11.2 Potential Benefits to Others

This study addresses one of the key barriers to implementation of MAT within efforts to expand MAT into underserved communities and primary care settings, namely the need to deliver evidence-based psychosocial treatment to help prevent relapse and foster a healthy lifestyle when behavioral health specialists are rarely co-located. Since reSET-O is a commercially mobile app, downloadable from the web, if found effective in supporting MAT in the Hub and Spoke setting under this research, it has the potential to be rapidly implemented across the U.S. health system in support of the STR initiative.

12.0 Sharing Results with Subjects

N/A

13.0 Subject Payment and/or Travel Reimbursements

All patients will be compensated for their time spent completing research evaluations, with \$40 for the intake/baseline visit and \$25 for each of the week 4, 8, 12, and 24 research visits (regardless if all tasks are completed onsite or if some tasks are completed remotely). An extra \$25 will be provided at the week 8 or 12 visit, when a participant completes the qualitative interview. Since the qualitative interview is specific to the use of the reSET-O app, only subjects who have been assigned to TAU + reSET-O will participate in the qualitative interview. Thus, total compensation will be \$165 in the form of gift cards for individuals assigned to TAU + reSET-O, and the total compensation for individuals assigned to TAU alone will be \$140 in the form of gift cards.

Gift cards earned based on completed research appointments will be printed and handed to the participant or emailed to the participant – based on participant preference. If emailed, research assistants will follow-up with the participant to ensure that the gift card was received; however, it will be outlined in the consent form that “lost” gift cards will not be replaced. This study does not plan to use Greenphire because the ability to withdraw actual cash from the Greenphire card would allow a vulnerable patient with addiction to potentially withdraw money to purchase drugs or alcohol. Gift cards provided in this study are never associated with vendors that sell alcohol, drugs, or weapons (e.g., Target).

Additionally, patients assigned to TAU + reSET-O may receive contingency management rewards as part of the reSET-O application program. Participants also have the possibility of earning monetary prizes ranging from \$5 to \$100, in the form of a vendor gift card (e.g. Amazon or Starbucks), on a varying reinforcement schedule. Participants may earn prizes through a wheel-spin gaming system as coded within the app. Wheel-spins are earned from having favorable urine drug screens, meaning no illegal substance is present in the participant’s urine, and learning module (within the app) completion. Urine drug screens are evaluated based on urine screens collected at visits 4, 8, 12, and 24, in which the assessing clinician or research coordinator will use the Clinician Dashboard on the reSET-O app to activate the lottery-based reward. The reSET-O app will manage the administration and activation of lottery-based rewards for participant completed modules.

Half of the lottery-based rewards will be e-language positive reinforcement (i.e.: “Good Job!”). 41.8% of the rewards will be \$5 electronic gift cards; 8.0% of the rewards will be \$20 electronic gift cards; and 0.2% of the rewards will be \$100 electronic gift cards (see uploaded power point document as an example of e-gift card administration from the reSET-O app). All electronic gift cards are managed and administered by the reSET-O application and ultimate owners (Pear Therapeutics, Inc.). Participants may earn a maximum of approximately

\$599 if they earn all possible draws; however, based on prior experience with such schedules, we predict that they will likely earn about 45%-65% of possible earnings (approx. \$270-\$390).

Provider subjects will not be compensated.

14.0 Economic Burden to Subjects

14.1 Costs

N/A

14.2 Compensation for research-related injury

It is the policy of the institution to provide neither financial compensation nor free medical treatment for research-related injury. In the event of injury resulting from this research, medical treatment is available but will be provided at the usual charge. Costs for the treatment of research-related injuries will be charged to subjects or their insurance carriers.

15.0 Resources Available

15.1 Facilities and locations

The study sites will be the SAMHSA STR funded Pennsylvania Psychiatric Institute (PPI)-based Hub and Spoke system, called Pennsylvania Coordinated Medication Assisted Treatment (PACMAT), for which [name] is the Principal Investigator. The PACMAT PPI Hub is a new specialized Addiction Treatment Program at Pennsylvania Psychiatric Institute (PPI) in Harrisburg, PA, and Spokes are medical practices in the surrounding, largely rural counties of central Pennsylvania, including Dauphin, Cumberland/Perry, Franklin/Fulton, Lancaster, and Lebanon counties.

All research procedures will occur in a hybrid of remote and in person, depending on patient preference and the current COVID situation in Dauphin County, PA.

15.2 Feasibility of recruiting the required number of subjects

Since the opening of the PACMAT PPI Hub in and collaboration with spoke providers through RASE in November 2017, over 700 OUD patients have been treated at the PPI Hub, whereas Spoke providers have treated over 900 OUD patients collectively. The majority of this combined patient population use MAT. Thus, the patient flow appears adequate especially given the broad eligibility criteria. We are excited about our new collaboration with Just for Today for this research project as they have locations in several counties in southern Central Pennsylvania and have a broad reach of patients on MOUD.

15.3 PI Time devoted to conducting the research

20% research time

15.4 Availability of medical or psychological resources

Medical and psychological resources are available at PPI should a subject endorse suicidality on the PHQ-9 and subsequent C-SSRS. If a subject endorses suicidality, trained and certified research staff will administer the C-SSRS. If the C-SSRS administration determines that suicidal ideation and plan are present, then the research staff will contact a doctor or nurse practitioner to take over the evaluating situation. At the opioid treatment program at PPI, there are currently three medical doctors and one nurse practitioner.

15.5 Process for informing Study Team

N/A

16.0 Other Approvals

16.1 Other Approvals from External Entities

This study is being considered for funding through NIH and, as such, has undergone scientific review as part of the application approval process.

16.2 Internal PSU Committee Approvals

Check all that apply:

- Anatomic Pathology – **Penn State Health only** – Research involves the collection of tissues or use of pathologic specimens. Upload a copy of “HRP-902 - Human Tissue For Research Form” in CATS IRB.
- Animal Care and Use – **All campuses** – Human research involves animals and humans or the use of human tissues in animals
- Biosafety – **All campuses** – Research involves biohazardous materials (human biological specimens in a PSU research lab, biological toxins, carcinogens, infectious agents, recombinant viruses or DNA or gene therapy).
- Clinical Laboratories – **Penn State Health only** – Collection, processing and/or storage of extra tubes of body fluid specimens for research purposes by the Clinical Laboratories; and/or use of body fluids that had been collected for clinical purposes but are no longer needed for clinical use. Upload a copy of “HRP-901 - Human Body Fluids for Research Form” in CATS IRB.
- Clinical Research Center (CRC) Advisory Committee – **All campuses** – Research involves the use of CRC services in any way.
- Conflict of Interest Review – **All campuses** – Research has one or more of study team members indicated as having a financial interest.
- Radiation Safety – **Penn State Health only** – Research involves research-related radiation procedures. All research involving radiation procedures (standard of care and/or research-related) must upload a copy of “HRP-903 - Radiation Review Form” in CATS IRB.
- IND/IDE Audit – **All campuses** – Research in which the PSU researcher holds the IND or IDE or intends to hold the IND or IDE.
- Scientific Review – **Penn State Health only** – All investigator-written research studies requiring review by the convened IRB must provide documentation of scientific review with the IRB submission. The scientific review requirement may be fulfilled by one of the following: (1) external peer-review process; (2) department/institute scientific review committee; or (3) scientific review by the Clinical Research Center Advisory committee. NOTE: Review by the Penn State Health Cancer Institute (PSCI) Protocol Review Committee or the PSCI Disease Team is required if the study involves cancer prevention studies or cancer patients, records and/or tissues. For more information about this requirement see the IRB website.

17.0 Multi-Site Study

17.1 Other sites

N/A

17.2 Communication Plans

N/A

17.3 Data Submission and Security Plan

N/A

17.4 Subject Enrollment

N/A

17.5 Reporting of Adverse Events and New Information

N/A

17.6 Audit and Monitoring Plans

N/A

18.0 Adverse Event Reporting

18.1 Adverse Event Definitions

For drug studies, incorporate the following definitions into the below responses, as written:	
Adverse event	Any untoward medical occurrence associated with the use of the drug in humans, whether or not considered drug related
Adverse reaction	Any adverse event caused by a drug
Suspected adverse reaction	Any adverse event for which there is a reasonable possibility that the drug caused the adverse event. Suspected adverse reaction implies a lesser degree of certainty about causality than “adverse reaction”. 
 Reasonable possibility. For the purpose of IND safety reporting, “reasonable possibility” means there is evidence to suggest a causal relationship between the drug and the adverse event.
Serious adverse event or Serious suspected adverse reaction	Serious adverse event or Serious suspected adverse reaction: An adverse event or suspected adverse reaction that in the view of either the investigator or sponsor, it results in any of the following outcomes: Death, a life-threatening adverse event, inpatient hospitalization or prolongation of existing hospitalization, a persistent or significant incapacity or substantial disruption of the ability to conduct normal life functions, or a congenital anomaly/birth defect. Important medical events that may not result in death, be life-threatening, or require hospitalization may be considered serious when, based upon appropriate medical judgment, they may jeopardize the patient or subject and may require medical or surgical intervention to prevent one of the outcomes listed in this definition.
Life-threatening adverse event or life-threatening suspected adverse reaction	An adverse event or suspected adverse reaction is considered “life-threatening” if, in the view of either the Investigator (i.e., the study site principal investigator) or Sponsor, its occurrence places the patient or research subject at immediate risk of death. It does not include an adverse event or suspected adverse reaction that had it occurred in a more severe form, might have caused death.
Unexpected adverse event or Unexpected suspected adverse reaction.	An adverse event or suspected adverse reaction is considered “unexpected” if it is not listed in the investigator brochure, general investigational plan, clinical protocol, or elsewhere in the current IND application; or is not listed at the specificity or severity that has been previously observed and/or specified.

For device studies, incorporate the following definitions into the below responses, as written:

Unanticipated adverse device effect	Any serious adverse effect on health or safety or any life-threatening problem or death caused by, or associated with, a device, if that effect, problem, or death was not previously identified in nature, severity, or degree of incidence in the investigational plan or IDE application (including a supplementary plan or application), or any other unanticipated serious problem associated with a device that relates to the rights, safety, or welfare of subjects.
--	--

18.2 Recording of Adverse Events

N/A

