- The enrollment form collects information that is used by the PSC to verify the identity of the subject including the patient's first and last name, and a date of birth, which will be a "dummy" date of birth (i.e.: 01-001-1999; dd-mmm-yyyy). The first and last name of the participant is required because PPI Hub clinicians who are also part of the research team will not be able to identify their patients who are engaged in the app through the clinician dashboard via subject IDs due to the volume of patients seen. Thus, the PPI Hub providers need to be able to see participant patient names in their clinician dashboard in order to engage with subject about their app use. The PSC form clearly indicates that this individual is enrolled in a research study, which allows staff at the PSC and Pear Therapeutics, Inc. to understand that services are not to be billed to any insurance.
- A phone number is also required for the enrollment form, which may be a phone number most commonly used by the participant, or a phone number associated with a research assistant's office phone (for participants who do not have an operating phone number). The phone number is needed because the PSC will call the subject weekly to ensure that that the participant is able to use the app without technical difficulty. The participant may opt out of these calls, which will be outlined in the consent form. reSET-O, Pear Therapeutics, Inc. (owners of reSET-O), and other entities affiliated with reSET-O do not use phone numbers for any other purpose including selling the phone number to third parties, sales calls, etc.
- An email is also required for the enrollment form, which may be an email most commonly used by the participant, or the research coordinator/research assistant may help the participant set up a free email account for purposes of this study. An email is needed because should the participant forget their username and/or password to login to the app, they will be able to reset their login credentials via email. reSET-O, Pear Therapeutics, Inc. (owners of reSET-O), and other entities affiliated with reSET-O do not use email addresses for any other purpose including selling the email to third parties, marketing or other advertisements, etc.

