8.3 Statistical methods

Outcome Measures and Covariates

Primary outcome: The primary outcome will be a binary indicator of whether or not the patient is retained on MAT (methadone, buprenorphine, or buprenorphine-naloxone) treatment through 24 weeks. For those who drop out before 24 weeks, time (week) of dropout will be recorded, and they will be considered as not retained.

Secondary outcomes: 1) weeks of treatment retention (time to drop-out 0-24 weeks, survival; number of weeks retained, continuous); 2) urine-confirmed abstinence from opioids in the last 4 weeks (longitudinal (weeks 4, 8, 12, and 24), binary); 3) Days using opioids in the last 4 weeks (longitudinal, continuous); 4) Days using other drugs/alcohol in last 4 weeks (longitudinal, continuous); 5) coping strategies (CSS mean score; longitudinal, continuous); 6) social functioning (EuroQol, SCS, global scores and subscales; longitudinal, continuous); 6) overall mental health symptoms (K10; longitudinal, continuous); 7) HIV risk behavior—days in past 30 of vaginal or anal sex without a condom (longitudinal, continuous); Any needle sharing in past 4 weeks (longitudinal, binary); 7) Treatment satisfaction at week 24 (IAFF; continuous); 8) Serious adverse events (binary).

Additional variables: *Covariates, primary and secondary analyses:* Stratification factors: 1) any intravenous drug use (binary); 2) treatment with methadone vs buprenorphine at Hub vs buprenorphine at Spoke (categorical). *Moderators:* 1) both stratification factors will be explored as moderators; 2) demographic characteristics (gender, age, ethnicity etc.); 3) prescription opioid use only vs any heroin or fentanyl use (binary); 4) other substance use at baseline (any cannabis, any stimulant, any heavy drinking days; binary); 5) Probable major depression at baseline (binary based on PHQ score); 6) history of prior treatment for opioid use versus first treatment episode (binary). *Mediators:* 1) social functioning (EuroQol; continuous); 2) social connectedness (SCS; continuous); 3) opioid craving (continuous); 4) coping (CSS; continuous); and 5) mental health symptoms (K10; continuous).

Intent to Treat, Dropouts, and Missing Data

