Statistical Model: *Hypothesis: Adding reSET-O to TAU (reSET-O + TAU arm) will promote greater 24 week retention in treatment on buprenorphine compared to the TAU arm.* The positive effect of randomization to the reSET-O+TAU group compared to TAU group will be estimated using logistic regression with the binary outcome of retention in treatment for 24 weeks (yes/no) modeled as a function of treatment condition (reSET-O + TAU vs TAU) and stratification factors (methadone treatment; buprenorphine treatment at Hub; buprenorphine treatment initiation at hub and continuation at spoke) and intravenous drug use in last 30 days (yes/no). The odds ratio of the treatment term and its confidence limits will estimate the treatment effect. The raw retention rates in each treatment group and rate differences will be computed for descriptive purposes.

Secondary outcomes

Statistical Models: For each of the secondary outcomes (see above) the effect of randomization to the reSET-O+TAU arm compared to the TAU arm will be estimated with a model of the same general form as for the primary outcome (three independent variables: treatment assignments (reSET-O+TAU vs TAU) and the two stratification factors) using logistic regression model (for binary outcomes), generalized linear model (for continuous outcomes), or longitudinal generalized mixed effects model (for longitudinal outcomes) with appropriate link functions (e.g. logit for binary outcomes). Longitudinal outcomes analyzed using a mixed effects models will utilize a generalized estimating equation with an autoregressive correlation structure to account for within subject correlation over time, as well a random intercept accounting for between subject variability. Retention data will be displayed with Kaplan-Meier curves that show the observed probability of retention in the program until time t, over time across the 24-week trial. The time to not-retained (dropout) data for reSET-O +TAU and TAU groups will be analyzed using proportional hazards models with covariates. If proportional hazard assumption is not satisfied, the data will be analyzed using a non-parametric log-rank test. In addition to stratification factors, covariates that are found to be related to the outcomes will be also added to the models to improve the power for detecting significant differences.

Moderation and Mediation

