9.0 Data and Safety Monitoring Plan

9.1 Periodic evaluation of data

Data is directly entered into REDcap by the research assistants. The research coordinator will periodically check the data as it is entered to ensure REDcap is working properly and recording the data as appropriate. Regular quality assurance monitoring will be conducted by [name] (Columbia) who will remotely review regulatory documentation, data collection and data management procedures, and review other study documentation (e.g., progress notes, error corrections, contingency management logs). These reviews will also include: 100% review of informed consents, eligibility criteria, AE and SAE documentation, and protocol violations.

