9.3 Method of collection of safety information

Study progress and safety will be reviewed weekly via conference call with the Study PIs and research team. Progress reports, including patient recruitment, retention/attrition, and AEs, will be provided to PIs following each of the QA monitoring visits. An Annual Report will be compiled and will include a list and summary of AEs. The Annual Report will be submitted to the data safety monitoring board (DSMB), IRB and NCCIH per their requirements. The IRB and other applicable recipients will review progress of this study on an annual basis.

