19.1.2 Safety Monitoring

N/A

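### Serious adverse events are compared between arms, but the protocol does not say how they are elicited or recorded, so equal ascertainment cannot be assured

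*Combined protocol and SAP*

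**What the plan says.** Section 8.3 lists "8) Serious adverse events (binary" among the secondary outcomes, and its modelling paragraph states: "For each of the secondary outcomes (see above) the effect of randomization to the reSET-O+TAU arm compared to the TAU arm will be estimated". Binary outcomes get a logistic regression on treatment and the two stratification factors. SAEs are therefore a planned between-arm comparison as well as a safety listing.

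The entry under "18.2 Recording of Adverse Events" is N/A, and so is the entry under "19.1.2 Safety Monitoring".

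Section 9, the data and safety monitoring plan, does describe oversight. Section 9.1 provides for "100% review of informed consents, eligibility criteria, AE and SAE documentation, and protocol violations". Section 9.3 says "Study progress and safety will be reviewed weekly via conference call with the Study PIs and research team" and, on reporting, "The Annual Report will be submitted to the data safety monitoring board (DSMB), IRB and NCCIH per their requirements". Section 18.1 defines a serious event, Section 18.3 has the investigator assess documented events for causality and seriousness, and Section 18.5 covers reporting to the IRB.

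Contact differs by arm. Section 7.3 gives all participants five research visits and two check-in calls. In the reSET-O arm only, Section 7.2.1 adds that "the PSC will call the subject weekly" about technical use of the app, with the right to opt out. That arm also has recorded interviews (Section 7.2.2), longer visits (Section 7.3) and dashboard discussions with providers (Section 4.1).

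**The concern.** A between-arm comparison of event counts is interpretable only if both arms are asked the same thing, at the same times, over the same period. The protocol defines an SAE and says who reviews one. It does not say who asks, with what question or form, at which contacts, over what look-back window, or what happens after a patient leaves treatment. Staff who follow the plan as written have no uniform capture procedure.

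This matters more here because participants and site staff know the assignment (blinded assessment is specified only for the follow-up TLFB, Sections 7.2.1 and 7.4.5) and because one arm has more occasions on which an event might come to light. At stake are the SAE odds ratio and the completeness of the adverse event summary sent to the DSMB. The primary retention outcome is not touched.

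**Working it through.** **Step 1. Does any section supply the missing method?**

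- Section 9.1: reviews documentation that already exists.
- Section 9.3: its title promises a method of collecting safety information, but the text covers weekly calls, progress reports and the annual report.
- Section 18.3: starts from documented events.
- Section 18.5: applies a filter (unexpected and probably related) to events already observed or reported.
- Section 18.2: the natural place for the method, and it is N/A.

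Every step lies downstream of recording. A complete review of the records cannot find an event that nobody asked about.

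**Step 2. Do the visit instruments supply it?** Section 7.2.1 lists no AE or SAE form. Two items come near:

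- Overdose History asks about overdose at any time in life, with follow-up detail. Section 7.2.2 repeats the listed measures at weeks 4, 8, 12 and 24 without restriction by arm.
- The C-SSRS is triggered by one PHQ item. The PHQ is described as a baseline screen, although Section 7.2.2 repeats the measures in general terms.

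The TAU Tracking Form logs treatment services received and is not described as asking about hospital care. None of these covers the seriousness criteria in Section 18.1, such as inpatient hospitalisation. With no scheduled question, the absence of a report also cannot be told apart from the absence of an event.

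**Step 3. Contacts.** Shared research contacts: 5 visits + 2 calls = 7. Weekly vendor calls over 24 weeks add at most 24 in the reSET-O arm, fewer with opt-out. The interviews lengthen existing visits and do not add to that count.

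**Step 4. The plan's only design figure.** Section 8.2: 40% vs 59.7%, 80% power, two-sided 5%. With mean proportion 0.4985 and pooled variance,

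n = [1.960 × √(2 × 0.4985 × 0.5015) + 0.8416 × √(0.40 × 0.60 + 0.597 × 0.403)]² / 0.197² = (1.386 + 0.583)² / 0.0388 ≈ 100 per arm,

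and the odds ratio is (0.597/0.403)/(0.40/0.60) = 2.22. Both agree with the plan. No rate, precision or power is stated for SAEs.

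**Step 5. Illustration of unequal capture.** The documents give neither an SAE rate nor a capture probability, so every input here is assumed. Observed risk = true risk × capture. Take a true risk of 10% in both arms (true odds ratio 1.0), 100 patients per arm and 90% capture in reSET-O, so that 0.10 × 0.90 = 9%. The last column is the normal-approximation chance of a significant excess in the reSET-O arm, against a nominal 2.5%.

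| TAU capture | Observed TAU | Observed reSET-O | Odds ratio | Chance of false excess |
|---|---|---|---|---|
| 80% | 8% | 9% | (0.09/0.91)/(0.08/0.92) = 1.14 | 4.4% |
| 70% | 7% | 9% | (0.09/0.91)/(0.07/0.93) = 1.31 | 7.5% |
| 50% | 5% | 9% | (0.09/0.91)/(0.05/0.95) = 1.88 | 19.7% |

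Equal capture, for example 70% in both arms, gives 1.00. Over true risks of 5% to 20% and the same capture pairs, the odds ratio runs from 1.13 to 1.98. If capture were instead better in TAU, the ratios in the table become reciprocals: 1/1.14 = 0.88 to 1/1.88 = 0.53. A real benefit could also be hidden: a true 20% vs 14% (odds ratio 0.65) with 50% vs 90% capture is seen as 10% vs 12.6%, an odds ratio of 1.30.

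**The case against.** Four points can fairly be made for the plan.

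- **Oversight exists.** A reader of the N/A under Section 19.1.2 might infer that the trial has no safety monitoring. Section 9 contradicts that: weekly safety review, full review of AE and SAE documentation, and annual reporting to the DSMB. What stands is an inconsistency between the two sections and the absence of an elicitation method.
- **Capture may be more even than the contact count suggests.** A reader might infer that SAE capture rests on spontaneous reports and must inflate the reSET-O count. The documents do not say that reporting is spontaneous. Patients in both arms have a case manager who meets them regularly (Section 1.1) and routine urine testing (Section 7.2.1), and treating clinicians are on the study team (Section 4.1). The vendor calls concern technical problems, can be declined, and are nowhere linked to adverse event records. Better retention in one arm could also shift capture either way. So the direction of any bias is not established.
- **Patients who leave treatment are not simply lost.** The Locator form in Section 7.2.1 exists so that they can be found and assessed, and the week 16 and 20 calls apply to everyone. But neither is given an SAE question.
- **The effect may be small.** With 9 vs 7 events per 100, z = 0.02/√(2 × 0.08 × 0.92/100) = 0.52, well within chance, and Section 10.0 describes a low-risk behavioural intervention. This limits the importance of the point but does not supply a recording method.

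**Conclusion.** The point holds as a gap in ascertainment. SAEs are a planned between-arm outcome, their recording section is N/A, and nothing else in the protocol says how they are elicited. In an open-label trial with unequal contact, equal ascertainment cannot be assured and the comparison could be biased.

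The documents do not support saying that it will be biased, or in which direction. The odds ratios of about 1.1 to 1.9 rest wholly on an assumed 10% true risk and assumed capture of 90% vs 50% to 80%. They show what unequal capture could do and are not an estimate for this trial. The consequence is limited to one secondary safety outcome and the DSMB summaries.

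**What to change.** 1. Replace N/A in Section 18.2 with one scripted AE/SAE question set covering hospitalisation, emergency care, overdose and death, with the same look-back window in both arms. Ask it at weeks 4, 8, 12 and 24 and at the week 16 and 20 calls. Include patients who have left treatment but can be reached through the Locator form.
2. Keep every known SAE in the safety outcome and in DSMB reports, however it was learned, and record its source. Restricting the outcome itself to common-source events could drop a known death or hospitalisation.
3. Add to Section 8.3 a sensitivity analysis restricted to events from sources common to both arms.
4. Reconcile Section 19.1.2 with Section 9 by cross-reference.

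Cost: a short form, a few minutes at each existing contact, and text edits in Sections 8.3, 18.2 and 19.1.2. No visits are added, and the primary analysis, significance level and sample size do not change.
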